#### 12.1.1.2. Sample Size – Primary Device Performance Endpoint

The sample size calculation for the primary device performance endpoint is based on the following assumptions.

- Expected 30-day mean pressure gradient from Lotus Valve  $\leq 15$  mm Hg (based on the aforementioned literature review)
- Expected standard deviation = 7 mm Hg
- Performance goal (PG) = 18 mm Hg
- Test significance level ( $\alpha$ ) = 0.025 (1-sided)
- Power  $(1 - \beta) \geq 80\%$
- Evaluable number of subjects = Minimum of 49 subjects
- Expected rate of attrition = 15% (9 subjects)

Given the above assumptions, the planned enrollment will be up to 120 subjects. Two planned interim analyses based on the primary device performance endpoint at 30 days post-implant procedure will be performed on the first 40 and 60 enrolled subjects. Enrollment of a total of 120 subjects is planned to meet regulatory requirements. A final analysis will be carried out on the fully enrolled main trial cohort.

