REPRISE II: Repositionable Percutaneous Replacement of Stenotic Aortic Valve through Implantation of Lotus™ Valve System – Evaluation of Safety and Performance	
	
EC22. Current problems with substance abuse (e.g., alcohol, etc.).
 
EC23. Subject is participating in another investigational drug or device study that has not reached its primary endpoint.
 
EC24. Subject has untreated conduction system disorder (e.g., Type II second degree atrioventricular block) that in the opinion of the treating physician is clinically significant and requires a pacemaker implantation.
 
d: An alternative P2Y12 inhibitor may be prescribed if subject is allergic to or intolerant of clopidogrel.

Statistical Methods – Main Trial Cohort (N=120)	
Primary Statistical Hypothesis	Mean aortic valve pressure gradient at 30 days post implant procedure is less than the performance goal (PG) of 18 mmHg
Statistical Test Method	
A one-sample t-test will be used to test the one-sided hypothesis:
 
H0: Gradient30D ≥ PG
 
H1: Gradient30D < PG
 
where Gradient30D is the 30-day mean aortic valve pressure gradient for the Lotus Valve and PG is 18 mmHg.

Sample Size Parameters	
 
• Expected 30-day mean pressure gradient from Lotus Valve ≤15 mmHg
 
• Expected standard deviation = 7 mmHg
 
• PG = 18 mmHg
 
• Test significance level (<math>\alpha</math>) = 0.025 (1-sided)
 
• Power ≥ 80%
 
• Evaluable number of subjects = Minimum of 49 subjects
 
• Expected rate of attrition = 15% (9 subjects)
 
• Planned enrollment of up to 120 subjects
 
• Two planned interim analyses will be performed on the first 40 and 60 subjects enrolled based on the primary endpoint at 30 days post-implant procedure
 
• A final analysis will be performed on all subjects enrolled in the main trial cohort (120 subjects)
 
• The primary analysis population for the primary endpoint will be the
 

REPRISE II: Repositionable Percutaneous Replacement of Stenotic Aortic Valve through Implantation of Lotus™ Valve System – Evaluation of Safety and Performance	

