## **12. Statistical Considerations**

### **12.1. Endpoints**

#### **12.1.1. Primary Endpoints**

##### **12.1.1.1. Primary Device Performance Endpoint**

The study is powered to assess the primary device performance endpoint, which is the mean aortic valve pressure gradient at 30 days post implant as measured by TTE and assessed by an independent core laboratory. The null and alternative hypotheses for the primary device performance endpoint are as follows.

$$H_0: \text{Gradient}_{30D} \geq \text{PG}$$

$$H_1: \text{Gradient}_{30D} < \text{PG}$$

where  $\text{Gradient}_{30D}$  is the 30-day mean aortic valve pressure gradient for the Lotus Valve and PG is the performance goal (18 mm Hg).

Testing will be done for the primary device performance endpoint as described in the statistical analysis plan. A one-sample  $t$ -test will be used.

For the one-sample  $t$ -test, the test statistic is  $t = \frac{\bar{x}_{30D} - PG}{s_{\bar{x}}}$ ,

where  $\bar{x}_{30D}$  is the sample 30-day mean aortic valve pressure gradient,

$PG$  is the performance goal,

$s_{\bar{x}} = \frac{1}{\sqrt{N}} \left( \sqrt{\frac{\sum (x - \bar{x}_{30D})^2}{N-1}} \right)$  is the sample standard error,

$x$  is the 30-day mean aortic valve pressure gradient per subject, and

$N$  is the sample size.

The degrees of freedom used in this test is  $N - 1$ .

Two interim analyses will be conducted on the first 40 and 60 subjects and a final analysis will be conducted on the main trial cohort ( $N=120$ ). The alpha-level for the interim and final analyses is adjusted using the Pocock alpha spending function method for unequal information time intervals; they are 0.01123, 0.00792, and 0.01305, respectively. If the  $P$  value from the one-sample  $t$ -test is  $< \alpha$ , the Lotus Valve will be concluded to have a 30-day mean aortic valve pressure gradient  $< 18$  mm Hg. This corresponds to the one-sided upper  $(1 - \alpha)\%$  confidence bound of the observed 30-day mean aortic valve pressure gradient being  $< 18$  mm Hg.

A sensitivity analysis (tipping-point analysis) will be performed to assess the impact of subjects with inadequate follow-up (i.e., missing data) on the primary device performance endpoint and to assess the robustness of the conclusion of the primary analysis.

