#### **12.3.2. Interim Analyses**

**12.3.3. There are 2 planned interim analyses for CE Mark dossier submission purposes. They will be based on the primary device performance endpoint at 30 days post-implant procedure and will be performed on the first 40 and 60 enrolled subjects. The final analysis of the primary device performance endpoint will be conducted on the fully enrolled main trial cohort (N=120). The Pocock alpha spending function method for unequal information time intervals is used to adjust the alpha-level for each analysis: 0.01123, 0.00792, and 0.01305, respectively. Justification of Pooling**

The analyses will be presented using data pooled across institutions as well as by center for the primary device performance endpoint and the primary safety endpoint.

Assessments of the poolability of subjects across centers will be made using the Chi-square test to determine if there is a relationship between the center and the primary safety endpoint,

and analysis of variance (ANOVA) to test for differences in the means of the primary device performance endpoint across centers. If the  $P$  value for the Chi-square test or ANOVA is  $\geq 0.15$ , the data can be pooled across that center. In the analysis to justify pooling across centers, the centers with fewer than 5 subjects enrolled in the study will be combined into “virtual centers” based on geographic region so that “virtual centers” have  $\geq 5$  subjects in the study but no more than the largest enrolling center.

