11. Study Methods Table 11.1-1  and Section 11.4 Screening Assessments	
l: A coronary angiogram must be performed within 180 days prior to the index procedure and should be performed within 90 days, if possible, to assess extent of aortic stenosis and coronary artery status.
 
o A coronary angiogram must be performed within 180 days prior to the index procedure and should be performed within 90 days, if possible; simultaneous aortogram and hemodynamics indicating ascending aorta/left ventricle (AO/LV) pressure measurements should be performed to assess the extent of aortic stenosis and coronary artery status.
	
l: A coronary angiogram must be performed within 365 days prior to the index procedure. If there is concern regarding the current extent of coronary artery disease or aortic stenosis, the Case Review Committee may recommend a repeat study closer to the time of enrollment.
 
o A coronary angiogram must be performed within 365 days prior to the index procedure. If there is concern regarding the current extent of coronary artery disease or aortic stenosis, the Case Review Committee may recommend a repeat study closer to the time of enrollment. An aortogram and hemodynamics including simultaneous ascending aorta and left ventricle pressure measurements should be performed during the cardiac catheterization.
	Expanded window allowed for coronary angiogram so as to minimize the need for unnecessary repetition of invasive tests in an elderly patient population while still ensuring that adequate assessment of coronary artery disease and aortic stenosis is performed. Note that similar change is made in Section 11.4 Screening Assessments (Imaging assessments).

Table 27.1-4: Table of Changes for REPRISE II Protocol Version AE (Compared to REPRISE II Protocol Version AD)			
Section Modified	Text as Written in REPRISE II Protocol Version AD	Text as Written in REPRISE II Protocol Version AE	Justification for Modification
2. Protocol Synopsis, Sample Size Parameters	
 
• Test significance level (<math>\alpha</math>) = 0.05 (1-sided)
 
• Power <math>\geq</math> 90%
 
	
 
• Test significance level (<math>\alpha</math>) = 0.025 (1-sided)
 
• Power <math>\geq</math> 80%
 
	Updated per regulatory agency request.

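### Does the minimum of 49 evaluable subjects for the gradient endpoint fail to follow from its stated 0.025 and 80% inputs?

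*Combined protocol and SAP*

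**What the plan says.** Section 12.1.1.2 (repeated under Sample Size Parameters in the synopsis) lists the assumptions for the primary device performance endpoint. The synopsis gives "Expected 30-day mean pressure gradient from Lotus Valve ≤15 mmHg"; both places add an SD of 7 mmHg, a performance goal of 18 mmHg, a one-sided significance level of 0.025 and power of at least 80%. The result is "Evaluable number of subjects = Minimum of 49 subjects", followed by "Expected rate of attrition = 15% (9 subjects".

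The same section then plans up to 120 subjects, with interim analyses on the first 40 and 60, and gives the reason for the total: "Enrollment of a total of 120 subjects is planned to meet regulatory requirements". Section 12.1.1.1 specifies a one-sample t-test. It adjusts the level at the three analyses by a Pocock spending function for unequal information intervals: "they are 0.01123, 0.00792, and 0.01305, respectively". Section 12.3.2 adds the purpose of the early looks: "There are 2 planned interim analyses for CE Mark dossier submission purposes".

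Table 27.1-4 in the change log records that alpha and power moved from 0.05 and 90% to 0.025 and 80%, with the reason "Updated per regulatory agency request". It lists no change to 49 or to 9.

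**The concern.** A reader checking section 12.1.1.2 will usually start with a single one-sample t-test at 0.025 and 80% power. That gives 45 evaluable subjects, not 49, and 8 lost to attrition, not 9. The same formula with the superseded 0.05 and 90% gives exactly 49. Since the change log alters alpha and power but not the 49, the natural inference is that the sample size was left behind when its inputs changed.

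Two further points add to the suspicion. No analysis is planned at 49 subjects, and no look is tested at 0.025. The section also states no power for the looks at 40, 60 and 120, although the first two support a regulatory submission. If the figure were wrong, the sample-size justification of a primary endpoint could not be reproduced from its own assumptions.

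**Working it through.** **Inputs.** From 12.1.1.2: difference δ = 18 − 15 = 3 mmHg, σ = 7 mmHg, overall one-sided α = 0.025, power at least 80%, attrition 15%. From 12.1.1.1: looks at 40, 60 and 120, so information fractions t = 1/3, 1/2 and 1, with one-sided levels 0.01123, 0.00792 and 0.01305.

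**1. Three-look calculation.** At look k the test statistic is approximately normal with mean θ√t_k and variance 1, where θ = (δ/σ)√N. The correlation between looks j < k is √(t_j/t_k).

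- Critical values from the stated levels: 2.282, 2.413 and 2.225.
- Correlations: √(2/3) = 0.816 (looks 1 and 2), √(1/3) = 0.577 (1 and 3), √(1/2) = 0.707 (2 and 3).
- Overall type I error, setting θ = 0: 0.0249. The stated levels therefore use up the 0.025 of section 12.1.1.2, which is the overall level.
- At N = 49, θ = (3/7) × 7 = 3.000, so the means at the looks are 1.732, 2.121 and 3.000.

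Power is one minus the probability that all three statistics stay below their critical values, by trivariate normal integration:

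| Maximum evaluable N | Power over three looks |
|---|---|
| 45 | 76.4% |
| 48 | 79.2% |
| **49** | **80.04%** |

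The exact solution for 80% is 48.95, which rounds up to 49. As a cross-check, the fixed-sample normal size is ((1.960 + 0.842) × 7/3)² = 42.73. The ratio 48.95/42.73 = 1.146 is the inflation that these boundaries require.

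**2. Attrition.** 49/0.85 = 57.6, rounded up to 58; 58 − 49 = 9. This is the plan's figure.

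**3. Single-test calculation.** By the noncentral t distribution with effect size 3/7:

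| α (one-sided) | N | Power |
|---|---|---|
| 0.025 | 44 | 79.4% |
| 0.025 | 45 | 80.3% |
| 0.025 | 49 | 83.6% |
| 0.05 | 48 | 89.99% |
| 0.05 | 49 | 90.5% |

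So 45 is right for one test at 0.025 and 80%, and 49 is right for one test at 0.05 and 90%. But the plan does not describe one test, and 12.1.1.2 nowhere says that its N is for one. Even on the single-test reading, 49 satisfies the requirement of at least 80%.

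**4. The trial as planned.** Simulation of the three t-tests (400,000 trials per scenario, SD 7) gives cumulative power at looks 1, 2 and 3:

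| True mean | Evaluable at looks | Cumulative power |
|---|---|---|
| 15 | 40/60/120 (no attrition) | 63.2%, 82.1%, 99.3% |
| 15 | 34/51/102 (15% attrition) | 54.7%, 74.5%, 98.2% |
| 14 | 34/51/102 (15% attrition) | 82.0%, 94.8%, over 99.9% |

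Simulated overall type I error at the stated levels is about 0.025 in both attrition scenarios.

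**The case for a change.** The strongest counter-argument is that 49 is a leftover. It equals the single-test minimum under the superseded inputs, and the log shows no change to it. The earlier value also does not look group-sequential: with the superseded levels 0.02246, 0.01704 and 0.02799 (also in Table 27.1-4), the calculation in step 1 at N = 49 gives 87.8%, short of the 90% then required. So 49 may well have entered the plan as a single-test figure.

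That explanation remains possible. It does not show an error, because an unlogged 49 is what one would see either if nobody recalculated it or if recalculation under the new inputs returned the same number. The documents cannot separate the two, and the current text is what has to stand up. It does.

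A second objection is that the test is a t-test, while step 1 uses normal theory. Simulating the three looks with t-tests at one third, one half and all of N gives 77.7% at 49 and first passes 80% at 52. This is correct as a small-sample refinement, but group-sequential sizes are commonly computed by normal theory, and a gap of 3 subjects is immaterial when 120 are planned.

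It is also true that the plan neither shows the derivation of 49 nor states power at each look. Interim power below 80% arises at the first look if the true mean is at the upper limit of 15, and at the second only if there is attrition as well. Missing an interim boundary does not end the test.

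**Conclusion.** The concern does not hold. Under the stated difference of 3 mmHg, SD of 7, overall one-sided 0.025 and the stated three-look boundaries, 49 is the smallest maximum sample size that reaches 80% power (80.04%, against 79.2% at 48), and the 9 subjects for attrition follow from it. This rests on normal theory and on a true mean of exactly 15. Replacing 49 by the single-test figure of 45 would lower three-look power to about 76%, below what the plan requires.

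What is left is an undocumented derivation and the absence of look-by-look power. Neither changes a result: enrolment is 120 for regulatory reasons, power over the three looks is about 98% with 15% attrition and 99% with none, and the overall type I error is 0.025 as intended.

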#### 12.1.1.3. Primary Safety Endpoint

Subsequent to the enrollment of the main trial cohort for device performance assessment (see Section 12.1.1.2), up to 130 more subjects will be enrolled in the extended trial cohort to perform a statistically powered assessment of the primary safety endpoint. The null and alternative hypotheses for the primary safety endpoint are as follows.

$$H_0: \text{Mortality}_{30D} \geq PG$$

$$H_1: \text{Mortality}_{30D} < PG$$

where  $\text{Mortality}_{30D}$  is the 30-day all-cause mortality rate for the Lotus Valve and PG is the performance goal.

Testing will be done for the primary safety endpoint as described in the statistical analysis plan. A one-sample  $z$ -test will be used, the  $z$ -test statistic is  $z = \frac{P_{30D} - PG}{s_p}$ ,

where

$P_{30D}$  is the sample 30-day all-cause mortality rate,

$PG$  is the performance goal,

$s_p = \sqrt{\frac{P_{30D}(1 - P_{30D})}{N}}$  is the sample standard error,

$N$  is the sample size.

A sensitivity analysis (tipping-point analysis) will be performed to assess the impact of subjects with inadequate follow-up (i.e., missing data) on the primary safety endpoint and to assess the robustness of the conclusion of the primary analysis.

The sample size calculation for the primary safety endpoint is based on the following assumptions.

- Expected 30-day all-cause mortality rate = 9.8%
- Performance goal (PG) = 16 % (expected rate of 9.8% + testing margin of 6.2%)
- Test significance level ( $\alpha$ ) = 0.025 (1-sided)
- Power ( $1 - \beta$ ) = 80%
- Expected rate of attrition = 2%

If the  $P$  value from the one-sample  $z$ -test is  $<0.025$ , it will be concluded that the primary safety endpoint for the Lotus Valve is less than the PG. This corresponds to the one-sided upper 97.5% confidence bound of the observed 30-day mortality rate being  $<16\%$ .

The expected rate of 9.8% for 30-day all-cause mortality is based on a literature review. Given the above assumptions, 233 subjects will be required. In order to account for a 5% expected rate of attrition, a total of 250 subjects is required for the planned hypothesis testing.

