	
subject population implanted with the Lotus Valve.
 
Note 1: The expected 30-day mean aortic valve pressure gradient is assumed to be <math>\leq 15</math> mmHg based on a literature review of studies evaluating the Medtronic CoreValve System and the Edwards Lifesciences SAPIEN Transcatheter Heart Valve System.
 
Note 2: The alpha-level for the interim and final analyses of the main trial cohort is adjusted using the Pocock alpha spending function (see Success Criteria below).

Success Criteria	
Two interim analyses will be conducted on the first 40 and 60 subjects and a final analysis will be conducted on the fully enrolled main trial cohort (N=120). The Pocock alpha spending function is used to adjust the alpha-level for each analysis: 0.01123, 0.00792, and 0.01305, respectively. If the P value from the one-sample t-test is <math>< \alpha</math>, the Lotus Valve will be concluded to have a 30-day mean aortic valve pressure gradient <math>< 18</math> mm Hg. This corresponds to the one-sided upper (1-alpha)% confidence bound of the observed 30-day mean aortic valve pressure gradient being <math>< 18</math> mmHg.

Statistical Methods – Combined Main and Extended Trial Cohort (N=250)	
Primary Statistical Hypothesis	All-cause mortality at 30 days post implant procedure is less than the PG of 16 % (expected rate of 9.8% + testing margin of 6.2%)
Statistical Test Method	
A one-sample z-test will be used to test the one-sided hypothesis:
 
<math>H_0</math>: Mortality30D <math>\geq</math> PG
 
<math>H_1</math>: Mortality30D <math><</math> PG
 
where Mortality30D is the 30-day all-cause mortality rate for the Lotus Valve and PG is 16%.

REPRISE II: Repositionable Percutaneous Replacement of Stenotic Aortic Valve through Iplantation of Lotus™ Valve System – Evaluation of Safety and Performance	

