Sample Size Parameters	
 
• Expected 30-day all-cause mortality rate = 9.8%
 
• Performance goal (PG) = 16 % (expected rate of 9.8% + testing margin of 6.2%)
 
• Test significance level (<math>\alpha</math>) = 0.025 (1-sided)
 
• Power (<math>1 - \beta</math>) = 80%
 
• Expected rate of attrition = 2%
 
• Planned enrollment of up to 250 subjects (main trial cohort enrollment of 120 subjects plus extended trial cohort enrollment of 130 subjects)
 
 
Note: The expected 30-day all-cause mortality rate is assumed to be 9.8% based on a literature review of studies evaluating the Medtronic CoreValve System and the Edwards Lifesciences SAPIEN Transcatheter Heart Valve System.

Success Criteria	
If the P value from the one-sample z-test is <math><0.025</math>, it will be concluded that the primary safety endpoint for the Lotus Valve is less than the PG. This corresponds to the one-sided upper 97.5% confidence bound of the observed 30 day mortality rate being <math><16</math> %.

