## 7. Endpoints

### 7.1. *Primary Endpoints*

The primary device performance endpoint is the mean aortic valve pressure gradient at 30 days post implant as measured by echocardiography and assessed by an independent core laboratory. The primary analysis population will be the subject population implanted with the

Lotus Valve. Outcomes in this as-treated subject population in the main trial cohort (N=120) will be compared to a performance goal (PG; see Section 12.1.1.1).

The primary safety endpoint is all-cause mortality at 30 days after the implant procedure. The primary safety endpoint will be evaluated on an intention-to-treat (ITT) basis (all subjects enrolled, whether or not a study device is implanted). Outcomes in the combined main and extended trial cohort (N=250) will be compared to a PG (see Section 12.1.1.3).

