#### 12.1.1.4. Statistical Methods

All subjects who are enrolled will be eligible for evaluation. Handling of dropouts and missing data will depend on their frequency and the nature of the outcome measure. The distribution of prognostic factors between subjects with and without data will be examined. Methods to eliminate or minimize bias will be implemented and described completely. Statistical models that account for censored data will be employed in appropriate circumstances (e.g., for time-to-event outcomes). Sensitivity analyses, including a tipping-point analysis for the primary endpoint, will be conducted to assess the impact of different assumptions on interpretation of the results. Outlier values will be evaluated for their validity. Suspected invalid data will be queried and corrected in the database prior to statistical analysis.

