#### 12.2.1. Analysis Sets

The primary analysis population for the primary device performance endpoint will be the subject population implanted with the Lotus Valve (as-treated subject population).

The primary safety endpoint will be evaluated on an ITT basis (all subjects enrolled, whether or not a study device is implanted). For the ITT analysis, all subjects who sign the written ICF and are enrolled in the study will be included in the analysis sample, regardless of whether the study device was implanted.

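### The primary safety z-test uses the standard error at the observed rate, so at N=250 its exact one-sided type I error is 3.1% and not the stated 2.5%

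*Combined protocol and SAP*

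**What the plan says.** The synopsis, for the combined cohort, states: "A one-sample z-test will be used to test the one-sided hypothesis", with null hypothesis mortality at or above 16%. Section 12.1.1.3 gives the statistic as the observed rate minus the goal, divided by the sample standard error "s_p = \sqrt{\frac{P_{30D}(1 - P_{30D})}{N". The rate in that expression is the observed one. The level is 0.025, one-sided, and success is P below 0.025. The section adds "This corresponds to the one-sided upper 97.5% confidence bound of the observed 30-day mortality rate being" below 16%, and the synopsis success criteria say the same.

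On sample size, with 9.8% expected mortality and 80% power: "Given the above assumptions, 233 subjects will be required". Enrolment is then set at 250 to allow for attrition. Section 7.1 fixes the comparison: "Outcomes in the combined main and extended trial cohort (N=250) will be compared to a PG". Section 12.2.1 fixes the population: "The primary safety endpoint will be evaluated on an ITT basis (all subjects enrolled, whether or not a study device is implanted").

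Section 12.1.1.3 refers to the statistical analysis plan for the testing, but the documents contain no other formula for this test.

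**The concern.** The type I error of a one-sample test against a fixed goal is set by how the statistic behaves when the true rate equals the goal. The standard error that belongs to that situation is the one at 16%. Using the observed rate makes the standard error shrink as the observed rate falls, and a low observed rate is what leads to a pass. The error therefore runs in one direction, in favour of the device.

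This is the only safety endpoint with a hypothesis test, and the extended cohort of up to 130 subjects is enrolled to power it. If the result falls at the boundary, the claim that mortality is below 16% would rest on the choice of standard error.

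**Working it through.** **Inputs** (Sections 12.1.1.3 and 7.1): goal p0 = 0.16; expected rate p1 = 0.098; one-sided alpha 0.025, so z = 1.960; planned N = 250; stated requirement before attrition 233.

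**The plan's own sample size.** The sizing method is not named.
- Printed observed-rate statistic: (1.960 + 0.842)² × 0.098 × 0.902 / 0.062² = 180.5, so 181 subjects.
- Goal-rate SE under the null and expected-rate SE under the alternative: 244.1, so 245.
- Arcsine formula: 226.3, so 227.
- Exact binomial test at n = 233: limit 26 deaths, power 79.3%.

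The stated 233 lies close to the arcsine and exact-test results and far from the 181 that the printed statistic would need. The sizing and the analysis formula therefore appear to use different methods.

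**Standard errors at 29 deaths of 250 (11.6%).**
- As written: sqrt(0.116 × 0.884 / 250) = 0.0203.
- At the goal: sqrt(0.16 × 0.84 / 250) = 0.0232.

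**Pass limit at N = 250 as written.**
- 29 deaths: z = (0.116 − 0.160) / 0.02025 = −2.173, P = 0.0149, upper bound 0.116 + 1.960 × 0.02025 = 15.57%. Pass.
- 30 deaths: z = −1.946, P = 0.0258, upper bound 16.03%. Fail.

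**Exact size.** P(X ≤ 29 | N = 250, p = 0.16) = 3.12%. The matching nominal 97.5% bound therefore covers 100 − 3.12 = 96.9% at a true 16%.

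**Results at N = 250 under each test:**

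| Test | P at 29 deaths | Upper bound at 29 | Pass limit | Size at 16% | Power at 9.8% |
|---|---|---|---|---|---|
| As written | 0.0149 | 15.57% | 29 | 3.12% | 85.6% |
| Goal-rate SE | 0.0289 | 16.16% (score) | 28 | 2.01% | 80.5% |
| Exact binomial | 0.0312 | 16.23% (Clopper-Pearson) | 28 | 2.01% | 80.5% |

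**How often the choice decides the result.** The probability of exactly 29 deaths of 250 is 5.1% at a true 9.8%, 7.7% at a true 12% and 1.1% at a true 16%.

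**Other N.** Repeating the calculation for each N from 233 to 250:
- As written: size 3.08% (N = 243) to 4.61% (N = 236), and 3.62% at N = 233.
- Exact test: size 1.58% to 2.42%.
- Goal-rate SE: same limit as the exact test except at N = 239 and 246, where its size is 2.52% and 2.57%.

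**Conditional on dropping subjects.** Section 12.1.1.3 gives attrition as 2% in its assumption list and 5% in its text. If subjects with unknown 30-day status were removed from N, the written rule's size would be 4.2% at N = 245 (2%) and 4.4% or 4.1% at N = 237 or 238 (5%). The documents do not say that such subjects are dropped.

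**The case against.** The strongest reply is that 0.025 is the nominal level of a large-sample test. The plan does not claim an exact binomial size. The printed test and its bound invert each other correctly, and the rule is explicit and prespecified. At N = 250 it differs from the alternatives at one count, which occurs in 1.1% of trials at a true 16%. The 5.1% and 7.7% figures describe cases where mortality truly is below 16%, so a pass there is a correct decision. A separate analysis plan might also specify something else.

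Much of this is fair as to size. The excess at N = 250 is small, a clearly low mortality passes under any of the tests, and the goal-rate SE is itself approximate. But the departure is one-sided, appears at every N from 233 to 250, and concerns a stated alpha that a text change would hold. The analysis-plan reference does not displace an explicit formula.

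It can also be said that missing 30-day status is a separate matter and should be rare, since Section 11.10.1 requires all enrolled subjects to be evaluated at 30 days and a tipping-point analysis is planned. That analysis addresses missing outcomes, not test size. The main finding does not depend on missing data.

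**Conclusion.** The concern holds. As written, the primary safety test has exact one-sided size 3.1% at N = 250 against the stated 2.5%. The practical difference there is one count, 29 deaths. The result rests on the printed formula, a true rate equal to the 16% goal, independent binomial outcomes and all 250 subjects in the denominator. With fewer evaluable subjects, down to 233, the size stays between 3.1% and 4.6%. This should be corrected before analysis. It does not undermine the design.

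**What to change.** In Section 12.1.1.3 and the synopsis, replace the z-test with an exact one-sided binomial test against 16% at 0.025, and report the Clopper-Pearson upper 97.5% bound. At N = 250 the pass limit becomes 28 deaths (exact P = 0.0201, bound 15.78%). As a minimum, keep the z-test but use sqrt(0.16 × 0.84 / N) as the standard error, with the matching score bound. The limit at N = 250 is the same.

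State in the same section how a subject with unknown 30-day vital status enters the rate and N. Section 12.1.1.4 leaves this open: "Handling of dropouts and missing data will depend on their frequency and the nature of the outcome measure". A stated rule fixes N and the pass limit in advance.

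The cost is protocol and SAP text plus a restated power figure. At N = 250, power at 9.8% falls from 85.6% to 80.5%, so the stated 80% holds without more subjects. Power moves in a sawtooth with N. Under the exact test it is 79.3% at 233, 76.7% and 76.0% at 237 and 238, 80.8% and 80.2% at 240 and 241, 77.7% at 245, and 82.2% falling to 80.5% over 247 to 250. The stated requirement of 233 would therefore need rewording, and dropping subjects at either stated attrition rate would take power below 80%. To hold 80% at that N and every larger one checked (up to 599) would need 262 evaluable subjects with the exact test, or 253 with the goal-rate standard error.
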